Depression and anxiety are common and debilitating disorders, both internationally (Eisenberg, Gollust, Golberstein, & Hefner, 2007; Hajduk, Heretik, Vaseckova, Forgacova, & Pecenak, 2019; Hasin, Goodwin, Stinson, & Grant, 2005; Hunt, Slade, & Andrews, 2004), and in South Africa (Herman et al., 2009). Among university students, symptoms of depression and anxiety are also very common (Bantjes et al., 2019) and are associated with significant problems including higher rates of academic failure and suicidal behaviours (Cranford, Eisenberg, & Serras, 2009; Eisenberg et al., 2007; Hysenbegasi, Hass, & Rowland, 2005). Despite viable psychotherapeutic and pharmacological options, the majority of depressed or anxious university students, like others in the general population, do not pursue treatment (Tolin, 2010; Trivedi et al., 2006; Wilson & Deane, 2010). Further, barriers to care, both those involving practical issues and psychological factors, lead to high attrition rates from treatment, resulting in modest effect sizes in effectiveness trials (Collins, Westra, Dozois, & Burns, 2004; Fergusson, Horwood, Ridder, & Beautrais, 2005). As a means of increasing accessibility and retention, effective psychological group interventions for symptoms of depression and anxiety have been developed and tested (Conley, Durlak, & Kirsch, 2015). Identifying individuals with a high likelihood of responding to psychological group interventions would enable clinicians to target this inexpensive treatment only to the patients with a high probability of responding; allowing more intensive treatments to be reserved for patients who would not respond to group-based skills training. The development of a system to make this determination would represent a major advance and address an unmet need. To date no attempts have been made to trial the use of psychological interventions for clinically significant symptoms of depression or anxiety among university students in South Africa. It is within this context that we propose a randomized controlled trial on the use of online group interventions for symptoms of depression or anxiety among university students in South Africa. The research project is a collaboration between the Centre for Student Counselling and Development at Stellenbosch University (SUN), the Institute for Life Course Health Research, Department of Global Health at SUN, and experts from the University of West Virginia and Harvard University.

METHODS

Study aims:

The specific aims of the study are:

- 1) Determine the proportion of university students who will utilize online psychological interventions for symptoms of depression and anxiety.
- 2) Determine if a 10-week online group CBT (GCBT) intervention effectively reduces symptoms of depression and anxiety among university students when compared with three control group interventions (i.e., Mood Flow, SilverCloud guided, and SilverCloud unguided).

This is a parallel group, unblinded randomized controlled trial (RCT), to assess the effectiveness of a novel 10-week online group CBT (GCBT) intervention that we have developed for university students reporting symptoms of depression or anxiety.

Students will be recruited from Stellenbosch University to participate in this RCT. Students will be sent an email invitation in randomized batches of 400 students at a time. The email will explain that we are conducting research on the use of digital interventions to reduce symptoms of depression and anxiety. The email will also invite students to enrol in the study by completing an online baseline assessment. Students will be asked to complete an Informed Consent Form before participating in the baseline assessment or any of the interventions. The Online Informed Consent Form outlines the primary aims of the study, inclusion/exclusion criteria, and rights as a participant (e.g., skip any question, discontinue at any time, right to withdraw) as well as detail about the online psychological group interventions. Students who meet the inclusion criteria will be randomized in a 1:1 ratio to one of the four study arms: the experiment group (i.e., the 10-week online GCBT intervention) or one of the three control groups (i.e., Mood Flow, SilverCloud guided, and SilverCloud unguided). We will repeat this recruitment strategy until we reach our target sample size of at least 400 students (i.e., a minimum of 100 students per intervention arm).

Students who enrol in the study will complete a baseline assessment prior to randomization. Follow-up assessments will also be conducted at 3-months, 6-months and 12-months post intervention. Assessment will consist of online self-report questionnaires administered using Qualtrics^{xM} software to record the following:

- (a) Respondent contact information
- (b) Background information

- (c) COVID-19
- (d) Physical health
- (e) Attention and concentration
- (f) Substance use
- (g) Symptoms of depression
- (h) Worry and anxiety
- (i) Panic attacks
- (j) Social anxiety
- (k) High mood
- (l) Obsessive-compulsive disorder
- (m) Stressful experiences
- (n) Other behavioural health problems
- (o) Self-harm
- (p) Personal relationships
- (q) Intervention evaluation for group therapy
- (r) Social networks
- (s) App and technology use
- (t) Treatment
- (u) Personality
- (v) Childhood experiences
- (w) University experiences

Inclusion Criteria:

- (a) Aged 18 or older years.
- (b) Enrolled as a student at Stellenbosch University.
- (c) Provide Informed Consent and completed baseline assessment.
- (d) Access to internet and a device that support apps.

Exclusion Criteria:

- (a) No internet availability or no device that supports apps.

Enrolment in group intervention:

Eligible students for the experiment group (i.e., online GCBT intervention) or control group (i.e., Mood Flow, SilverCloud guided, and SilverCloud unguided) will be sent an email inviting them to attend an online individual information session and briefing

about the group that they have been randomized to. The online individual information session will be conducted using the Microsoft Teams platform which is a free easy-to-use virtual meeting space. Information about the intervention they have been assigned to will also be sent via email.

No incentives will be paid for participating in the intervention.

Details of the online group CBT (GCBT) intervention:

The online GCBT intervention we have developed and previously piloted in a pragmatic trial (Bantjes et al., 2021), will be delivered via Microsoft Teams (a secure web-based video conferencing platform) in 10 weekly workshops of 60-75 minutes. The content was drawn from common elements identified from GCBT interventions shown to be effective for university students (Hamamci, 2006; Peden, Hall, Rayens, & Beebe, 2000; Takagaki et al., 2016; Yang, Zhao, Chen, Zu, & Zhao, 2018; Zemestani, Davoodi, Honarmand, Zargar, & Ottaviani, 2016). The content was organised into five themes with each theme spanning two workshops. To make the intervention more engaging and relevant to the target population, we consulted regularly over the development period with a group of four student advisors to select suitable examples, plan activities, and inform the lay-out and design of materials. Consultation with the student advisors took place in an iterative process over the course of a year while we developed and refined the intervention materials. We also consulted with three Psychologists working in student counselling centres and the intervention materials were critically reviewed by two CBT experts.

Participants assigned to the online GCBT intervention will be provided with electronic interactive pdf workbooks consisting of exercises and brief summaries of the main ideas and skills for each session before each workshop. Participants will be given the option to remain anonymous by keeping their web-cameras off and/or by using pseudonyms, although they will be encouraged to use web-cameras to show their faces during the workshops. Participants will also be invited to use the online chat function to type comments, questions, or responses during the sessions if they felt uncomfortable speaking in the group. Strategies that will be used to improve retention include giving participants permission to miss sessions but encouraging attendance at each new session, sending follow-up emails to students who missed

sessions prompting them to join the following week, and giving a brief recap of the previous workshop at the start of each new session.

Sessions will be facilitated by registered counsellors (the equivalent of psychological technicians with four years of university training) and registered psychologists. A facilitators' handbook, with detailed descriptions of the content of each session and facilitation guidelines will be provided and facilitators will be trained on group therapy facilitation. Online sessions will be recorded so that they could be reviewed during supervision.

Control groups:

The control groups will be directed to make use of one of three digital applications (apps); i.e., Mood Flow, SilverCloud (guided), and SilverCloud (unguided).

Assessment schedule:

As part of the study, the experimental group intervention participants will complete a baseline assessment at the start of the study and process assessments every two weeks. Follow-up assessment will also be administered to monitor symptom change (i.e., 3-month post-treatment, 6-month post-treatment, and 1-year post-treatment). The control group will only complete the baseline assessment and a 3-month follow up assessment.

Management of risk

If during the initial screening and recruitment or follow-up assessments, any participant endorses a "2" (more than half the days) or "3" (nearly every day) on the PHQ-9 (Thoughts that you would be better off dead or of hurting yourself in some way), they will receive an automated message that provides a list of emergency resources. The email and text message will be sent immediately after endorsing the item. Students who report active suicidality with intent at any time during the study will be referred to appropriate campus-based crises services, and national suicide helplines.

Statistical Analyses:

Data will be cleaned and analysed with SPSS (version 27). Descriptive statistics will be used to summarise participant characteristics, attendance rates, and primary outcomes.

We will evaluate aggregate intervention effects, as well as evaluate aggregate

differences across arms using conventional intent to treat (Gupta, 2011) and complier average causal effect (CACE) (Angrist, Imbens, & Rubin, 1996) analyses based on inverse probability weights to deal with loss to follow-up (Robins, Rotnitzky, & Zhao, 1994). Log-binomial regression will be used to estimate remission and to report adjusted prevalence ratios with 95% CIs. If convergence problems occur, we will fall back on Poisson regression with robust variance estimation. We will calculate numbers needed to treat for each outcome (remission of anxiety, depression, and combined PHQ-ADS). To estimate CACE, we will use two-stage least squares (Wooldridge, 2020) and control function procedures (Clarke & Windmeijer, 2012). We will evaluate the validity of the assumptions needed for this estimation and conduct sensitivity analyses. Distributions and correlates of dropout and missing data will be provided in reports.

Process analyses will allow us to investigate the pathways through which the intervention affects the outcomes by investigating intermediate effects of the individual intervention rule (IIR) in predicting responses in the five-minute process assessments that will be carried out every two weeks with students in the intervention arm over the 10 weeks of the intervention. The instrument used in these process assessments, the CBRSS (Miner, Schueller, Lattie, & Mohr, 2015), measures frequency of applying core cognitive skills (CSF) and core behavioral skills (BSF) during times of stress. We will also use the 4-item screening version of the GAD-7 and PHQ-9, the PHQ-4 (Kroenke, Spitzer, Williams, & Löwe, 2009), to assess anxiety-depression over each 2-week period. We will begin by investigating associations of the CSF and BSF measures both cross-sectionally and with a 2-week time-lag in predicting PHQ-9 scores. Our interest will be in determining whether CSF and BSF predictor PHQ-9 scores and if these associations increase over time.

We will also be interested in the associations of CSF and BSF data and individual differences in the slopes of PHQ-4 scores on CSF and BSF with the outcomes at the end of the intervention and in the 3-month, and 6-month follow-ups (i.e., academic attrition, performance, and engagement along with diagnostic classifications based on the GAD-7, PHQ-9, and PCL). We will also be interested in individual differences in mean values of CSF and BSF over the course of the intervention, changes (i.e., stronger changes in CSF and BSF over time for some students than others), and slopes of PHQ-9 scores on CSF and BSF scores in predicting long-term outcomes. We will be especially interested in the possibility of nonlinearities that document the existence of important minimum engagement

thresholds for achieving treatment effects (Chien et al., 2020). We will use a multilevel modelling framework to carry out these analyses. Finally, we will be interested in the extent to which the association of the IIR scores with long-term outcomes are mediated by the process measures obtained in the process assessments collected every two-weeks.

ETHICAL CONSIDERATIONS

Consent:

Eligible participants who satisfy the inclusion criteria and do not meet the exclusion criteria outlined in this proposal will be invited to participate in the online psychological group interventions and will be provided with an Online Informed Consent Form on participation in the research and online group intervention. The Online Consent Form outline: (a) aim of the research study, (b) risks and benefits of the research study, (c) assurance of confidentiality, (d) rights as a participant, including the right to refuse to answer any question, discontinue participation at any time, and withdraw from the study and (e) details on participating in online group interventions. No information obtained will be used without receiving the completed Informed Consent Form. After completing the consent form, participants will be emailed a pdf copy of the Informed Consent Form for their records.

Potential risks:

(a) *Privacy*. Participants who provided informed consent will be given details on the online intervention groups that they have been randomized to. Respective group facilitators will make a note of which students join which session as an online form of a register. Each participant will be assigned an alphanumeric ID so that data is stored in a way that is not directly linked to any identifying information.

All collected electronic data will be password protected and will be accessed only by authorized personnel. The data will only be used for this study and will be destroyed after a three-year period. Scientific publications or presentations on the results will only report analyses on an aggregated level.

(b) *Discomfort*. If participants experience discomfort when completing the study questionnaires or throughout the intervention, they can refuse to answer any questions. Further, all participants may choose to discontinue the assessment/intervention and/or withdraw from the study. This is outlined in the relevant Informed Consent Form.

Clinical Risk and Benefits. There are risks with any intervention, most specifically that they will not work or that a person might get frustrated by this intervention approach. However, there also are benefits as the group nature of this intervention shows students that they are not alone. There is no reason to believe this intervention would not prove effective in university students given past research showing that psychological group interventions in depressed and anxious higher education students are effective (Conley et al., 2015). Additionally, there are a number of benefits for the greater community. Namely, the study will advance our collective understanding of the feasibility in using psychological skills training group interventions for treating symptoms of depression and anxiety in university students. This information may then be utilized to develop more effective intervention programs.

Institutional permission:

We will seek institutional permission from the appropriate authorities at Stellenbosch University to conduct this study.

MONITORING, ASSESSMENT, AND RISK MANAGEMENT OF PARTICIPANTS

(a) The PIs will have the responsibility for continuous monitoring of data and safety of subjects in the study. Data and safety monitoring will take place continuously throughout the study's duration.

(b) Following the initial baseline assessment, those participants who report severe symptoms of depression, or suicidality will receive an automated message that provides a list of emergency resources.

- (c) Students' identified as being at risk will be immediately referred to the SSVO for further assessment and management. They will not be discharged from the RCT, but we will insist that they are also receiving individual care at the same time and that they are aware of the crises services available to students' (i.e. ER 24 crises line). The group facilitators will manage this referral process in collaboration with the SSVO.
- (d) All administrators will be trained and supervised by [name].
- (e) Of note, the administrators will not specifically probe or assess suicide risk. However, in the unlikely situation that a participant explicitly states that he/she is suicidal, the participant would be provided with a list of emergency resources, per email and phone text message.
- (f) We will report both adverse events and all serious adverse events that occur during the course of the study to the Institutional Review Board (IRB). Specifically, we will record all adverse events in a tracking log based on IRB templates, which will be submitted to the IRB at each continuing review.
- (g) At the time of the continuing review we will provide the IRB with a summary of any unexpected and related adverse events as well as any other unanticipated problems that occurred since the last continuing review.
- (h) Adverse events and unanticipated problems will be reported to the IRB per PHRC reporting guidelines. We will report to the IRB any unanticipated problems and adverse events that occur: (a) during the conduct of the study, (b) after study completion, or (c) after subject withdrawal or completion. Reports will be submitted within 5 working days/7 calendar days of the date the investigator first becomes aware of the problem.
- (i) Throughout the study there may be circumstances where a subject's participation may be terminated by the PI without the subject's consent. Specifically, potential reasons for participation termination may include: (a) increased participant suicidality, and (b) participant no longer satisfies inclusion criteria.

DATA STORAGE

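### GCBT runs in live groups, but its comparisons with the apps name no cluster unit; if delivery itself makes group members' outcomes alike, the planned 95% intervals are too narrow

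*Combined protocol and SAP*

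**What the plan says.** The unit of randomisation is the student. Under Methods: "Students who meet the inclusion criteria will be randomized in a 1:1 ratio to one of the four study arms".

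The arms differ in how they are delivered. The section on details of the GCBT intervention describes ten weekly live workshops on a video platform, led by registered counsellors and psychologists. The Control groups section assigns the other three arms to apps and describes no group sessions for them. The design is therefore partially nested, with groups in one arm only.

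The Statistical Analyses section then sets out the arm comparisons:

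- The framework covers "differences across arms using conventional intent to treat" and CACE "analyses based on inverse probability weights to deal with loss to follow-up".
- For remission: "Log-binomial regression will be used to estimate remission and to report adjusted prevalence ratios with 95% CIs".
- As fallback: "If convergence problems occur, we will fall back on Poisson regression with robust variance estimation".
- For compliers: "To estimate CACE, we will use two-stage least squares", together with control function procedures.

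No group term, facilitator term or cluster unit appears in any of these. The same section later says "We will use a multilevel modelling framework to carry out these analyses", but the analyses meant there are the process analyses of skill use and symptom slopes in the intervention arm.

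The documents do not say how GCBT groups are formed, how large they are, or whether they follow the recruitment batches.

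**The concern.** Students who share a facilitator and a set of peers may end up with more similar outcomes than students in different groups. If so, 100 GCBT students carry less information about the programme than 100 independent students, and a variance that treats them as independent is too small.

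The second study aim asks whether the GCBT programme reduces symptoms compared with the three apps. That is a question about the programme, not only about the particular groups and facilitators used. A 95% interval that ignores delivery-induced correlation would make a superiority claim for the experimental arm too confident. The point estimate is not in question, and comparisons among the app arms are not affected by GCBT groups.

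**Working it through.** **Inputs from the documents.** At least 400 students, with a minimum of 100 per arm (4 × 100 = 400); individual randomisation; groups in the GCBT arm only; 95% intervals, taken as a two-sided 5% test. The plan gives no ICC, design effect or group size, so it has no figure of its own to reproduce here.

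**Assumptions, none of them in the documents.** Allocated group size m = 8 to 15 (central 10); delivery-induced ICC = 0.01 to 0.10 (central 0.05); share attending a = 0.5, 0.7 or 1; remission 40% in the simulations. The null is one of real group effects that average to zero.

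**Step 1: formula.** Two members of an allocated group share a delivery effect only if both attend, so:

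- design effect in the GCBT arm: DE = 1 + (m − 1) × ICC × a²
- true over planned standard error, GCBT against one app arm of equal size: r = √((DE + 1)/2)
- actual error of the nominal 5% test: 2 × (1 − Φ(1.96/r))

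**Step 2: central case, m = 10, ICC = 0.05.**

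- a = 0.5: DE = 1 + 9 × 0.05 × 0.25 = 1.1125; r = 1.028; error 5.65%
- a = 0.7: DE = 1 + 9 × 0.05 × 0.49 = 1.2205; r = 1.054; error 6.29%
- a = 1: DE = 1 + 9 × 0.05 = 1.45; r = 1.107; error 7.66%

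**Step 3: range.**

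| m, ICC | a = 0.5 | a = 0.7 | a = 1 |
|---|---|---|---|
| 8, 0.01 | 5.10% | 5.20% | 5.40% |
| 10, 0.05 | 5.65% | 6.29% | 7.66% |
| 15, 0.10 | 7.06% | 9.08% | 13.28% |

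At ICC = 0, DE = 1, r = 1 and the error is 5.0%.

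**Step 4: simulation of the log prevalence ratio** (beta-binomial groups, 200,000 replicates). In the central case the unclustered error is 7.7% at full attendance and 5.6% at half, in line with the formula. Two-stage least squares for CACE gives 7.8% and 5.6%. Covariate-adjusted Poisson with inverse probability weights and 30% loss gives 6.7% at full attendance (60,000 replicates). The control function step was not simulated.

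**Step 5: correlation that is not due to delivery.** With an observed ICC of about 0.05 that comes only from how students are sorted into groups after randomisation, the planned unclustered test has 5.0% error. If it comes only from enrolment waves shared by all arms, the error is 4.4%. In neither case is the planned interval too narrow.

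**Step 6: the small-sample correction.** With clustering on the GCBT group, an arm-specific correction and Satterthwaite degrees of freedom, the error at full attendance is 4.5% (m = 10, ICC 0.05) and 4.9% (m = 15, ICC 0.10). If the correction counts every app student as a cluster, it nearly vanishes. The error is then 5.8% and 7.4% in those cases, and 8.2% at m = 20, ICC 0.05, where there are only five groups.

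**The case against.** The strongest case against is that nothing in the documents shows a delivery effect that differs between groups. A facilitators' handbook, facilitator training, session recordings used in supervision, and workbooks all point to uniform delivery. The benefit claimed for the group format would be common to every group, so it suggests an average effect rather than variation between groups. Students may miss sessions, keep cameras off and use pseudonyms, and the plan expects non-compliance because it includes CACE. Full attendance is therefore a poor central assumption, and at half attendance the inflation is well under one percentage point in the central case. All of this stands. It limits the size of the problem and the firmness of any claim, but it does not supply the missing cluster unit.

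Other parts of the plan do not supply it either. Robust variance is named only for the Poisson fallback, without a cluster, so it still treats students as independent. The multilevel framework belongs to the process analyses. The promised sensitivity analyses concern the CACE assumptions. The session register described under Potential risks records who joins a session, not who was allocated to a group. The remark there about groups that students were randomised to most naturally means study arms.

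A reader might infer that the planned test is invalid, or that its true error is about 8%. The documents do not support either. If GCBT changes nobody's outcome, individual randomisation keeps the error at about 5%, and the 8% figure depends on assumed inputs and full attendance. Nor does a positive observed ICC prove the point, because sorting after randomisation can produce one without harm. So can shared waves, which are possible because "Students will be sent an email invitation in randomized batches of 400 students at a time".

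**Conclusion.** The point holds conditionally. The ITT and CACE comparisons of GCBT with each app name no cluster unit, and if delivery itself creates within-group correlation, their 95% intervals are too narrow for inference beyond the groups run. At the assumed 10 per group and ICC 0.05, the effect is modest with partial attendance and reaches 7.7% error only with full attendance. The upper end of the range, 13.3%, needs 15 per group, ICC 0.10 and full attendance together. Group size, ICC, attendance and remission rate are all assumptions. The change is worth making because it is standard and cheap, and because the allocated group may be unrecoverable later for students who never attend. The evidence does not go further than that.

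**What to change.** State how GCBT groups are formed and their planned size. Record each GCBT student's allocated group at assignment; students never allocated to a group are singletons.

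For the GCBT-versus-app ITT and CACE comparisons, specify variance clustered on allocated group, with app students as singletons, and apply the small-sample correction by arm:

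- GCBT variance component: multiply by G/(G − 1), with G the number of GCBT groups
- app variance component: multiply by n/(n − 1), with n the number of students in that arm
- Satterthwaite degrees of freedom for the sum

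Say explicitly that G does not count app singletons. Keep the marginal prevalence ratio and number needed to treat as the estimand. Add no batch covariate: the documents plan none, and if groups coincide with batches, a batch covariate with clustering on the group alone can itself make intervals too narrow.

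The cost is an allocation log, one dataset column and one or two sentences in the Statistical Analyses section. Whether SPSS 27 provides clustered variance for the two-stage least squares and control function steps should be checked; other software may be needed. In the central case intervals become about 6% wider at half attendance and about 15% wider at full attendance. At ICC 0 they are about 2%-4% wider. If the correlation reflects only sorting or shared waves, the clustered analysis is conservative: error about 2.6%, with intervals 15%-16% wider for no gain.

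### Aim 2 asks about symptom reduction, but the only regression named for comparing arms is on three unranked, undefined remission outcomes; a baseline-adjusted PHQ-ADS score with a stated claim rule would answer it better

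*Combined protocol and SAP*

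**What the plan says.** - **Question.** Under Study aims, Aim 2 is to determine whether the 10-week GCBT course "effectively reduces symptoms of depression and anxiety among university students when compared with three control group interventions".
- **Outcomes.** The Statistical Analyses section promises that "Descriptive statistics will be used to summarise participant characteristics, attendance rates, and primary outcomes", but no outcome is named as primary anywhere.
- **Model.** The same section plans intent-to-treat and complier average causal effect (CACE) analyses with inverse probability weights for loss to follow-up. Remission is to be estimated by log-binomial regression, with robust Poisson as fallback, and then: "We will calculate numbers needed to treat for each outcome (remission of anxiety, depression, and combined PHQ-ADS". Two-stage least squares and control functions are named for CACE without an outcome scale. The multilevel models belong to the process analyses, whose two-weekly data come from the intervention arm alone.
- **Population.** The course is described as an "intervention that we have developed for university students reporting symptoms of depression or anxiety", yet the inclusion criterion that mentions the baseline questionnaire only asks that the student "Provide Informed Consent and completed baseline assessment". No symptom threshold is listed.
- **Timing.** The description under Study aims says "Follow-up assessments will also be conducted at 3-months, 6-months and 12-months post intervention" with no limit by arm. The Assessment schedule says "The control group will only complete the baseline assessment and a 3-month follow up assessment".

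**The concern.** Four choices are open at once: which of three remission outcomes leads, what cut-off defines remission, who is in the denominator, and which control contrasts must succeed. A student with few symptoms at baseline could count as remitted, as a non-event, or be left out, and the plan does not say which. The result that supports a claim of effectiveness could therefore be selected after the data are seen.

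Power is the second stake. Reducing a score to remitted or not remitted discards information. If remission carries the conclusion with about 100 students per arm against active comparators, a moderate benefit is more likely to be missed than with the score in the same students.

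**Working it through.** **Inputs from the documents.** Four arms, at least 100 per arm, at least 400 in total (4 × 100 = 400, which agrees). Three remission outcomes and three controls. No alpha, power, effect size, SD, remission rate or dropout rate is given, so the sample size cannot be derived from a power formula.

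**Assumed inputs.** Two-sided 5%; baseline-to-follow-up correlation r = 0.5; 40% control remission unless stated; 100 analysed per arm, with 70 as the lower case. Clustering is ignored until step 5.

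**1. False wins.** 3 outcomes × 3 controls = 9 tests. If independent, 1 − 0.95⁹ = 37.0% in either direction, but these tests share an arm and their outcomes are correlated. Simulating 20,000 null trials with a PHQ-9/GAD-7 correlation of 0.8 to 0.5, and PHQ-ADS as their sum, gives:
- any test favouring GCBT: 12.1% to 14.3%
- any test in either direction: 25% to 29%
- GCBT beating all three controls on some outcome: under 1%

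**2. Score against remission, same students, similar effect in all.** For the score, SE = √(2(1 − r²)/n). With n = 100 this is √(1.5/100) = 0.1225 SD. At 0.35 SD, 0.35/0.1225 = 2.86, which gives 81% power (noncentral t). Remission is simulated with baseline score as covariate and robust variance.

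| True effect | Remission | Score |
|---|---|---|
| 0.2 SD | 23% | 37% |
| 0.35 SD | 57% | 81% |
| 0.5 SD | 85% | 98% |

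A floor at zero narrows the gap. At 0.35 SD, remission against score is 57% vs 78% with 14% of students at zero, 53% vs 65% with 40%, and 40% vs 49% with 65%. At 0.2 SD with a floor the gain is only 3–12 points.

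**3. Only baseline cases benefit (0.5 SD in cases, none in others, no floor).**

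| Case share | Score, all | Remission, all | Remission, cases | Score, cases |
|---|---|---|---|---|
| 30% | 22% | 18% | 39% | 59% |
| 50% | 51% | 36% | 60% | 82% |
| 70% | 81% | 51% | 70% | 93% |

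Within the same students the score leads throughout. Across populations it need not: a score in all students loses to remission among cases at 30% and 50% cases.

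**4. Score power by claim rule (0.35 SD over every control, shared GCBT arm).**

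| Rule | 100 per arm | 70 per arm |
|---|---|---|
| One contrast at 5% | 81% | 66% |
| Each contrast, full Holm | 75% | 57% |
| Each contrast, Holm's strictest step (0.05/3) | 67% | 49% |
| Win over any control under Holm | 89% | 75% |
| Beat all three, each at 5% | 64% | 43% |

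Remission at Holm's strictest step has 38–40% power with 100 per arm and 25–27% with 70.

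**5. Clustering.** Assume ten GCBT groups of ten and an ICC of 0.05. The GCBT variance is multiplied by 1 + 9 × 0.05 = 1.45, so SE = √(0.75 × (1.45 + 1)/100) = 0.136. The 67% at Holm's strictest step falls to 57%, or 51% with small-sample degrees of freedom.

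**The case against.** **Aim 2 is not contradicted.** A reader might infer that the plan cannot answer its own question. The documents do not support that. Remission is one form of symptom reduction, a score model is not excluded, and the outcome scale for CACE is left open. The reference for control functions is titled for binary outcomes, but the one for two-stage least squares is a general text. The statement "Follow-up assessment will also be administered to monitor symptom change" precedes the sentence on controls and describes the GCBT arm, so it does not establish a planned between-arm score analysis either. This objection stands and limits the point to an omission.

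**The false-win rate depends on a rule the plan never states.** The plan promises prevalence ratios with 95% confidence intervals and numbers needed to treat, not a win on any of nine tests. This also stands: the range runs from under 1% to about 14%, and 12–14% must not be read as the plan's error rate.

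**A defined remission primary would also close the gap.** True for naming, cut-off and denominator. It would not recover the power lost within the same students. The objection does stand against any claim that a score in all students is always better (step 3).

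**A symptomatic population may be intended.** The introduction refers to clinically significant symptoms, and the risk section to initial screening. Still, the listed criteria contain no threshold, so the remission denominator remains unstated.

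**Conclusion.** The point holds as an omission worth correcting. The documents establish without any assumption that no primary outcome is named, the three remission outcomes are unranked and have no cut-off, eligibility sets no symptom threshold, no rule covers the three contrasts, and no between-arm score model is given.

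The sizes are conditional. Under the inputs above, the score gains about 24 points of power per contrast at 0.35 SD (81% against 57%), and less with many students at the floor. The ranking across populations turns on the baseline case share, which the documents do not give. A reader might also infer that 400 students are too few; since the plan states no target effect or power, that number can be neither confirmed nor called wrong.

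Timing matters too. The Assessment schedule counts the GCBT follow-up from the end of treatment but gives no anchor for the controls. After a 10-week course, the arms could be measured about 10 weeks apart relative to baseline.

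**What to change.** 1. Add a between-arm comparison of PHQ-ADS score at 3 months and make it the single primary analysis: students as randomised, linear regression on arm with baseline PHQ-ADS as covariate, the planned inverse probability weights, and standard errors that allow for GCBT group.
2. State the remission cut-off and prespecify the same score contrast among students above it at baseline. Before outcome data are seen, choose which of the two populations is primary, using the baseline case share pooled over arms, by a rule written down in advance.
3. State the claim: Holm over the three contrasts if a win over any one control counts, or each at 5% without correction if GCBT must beat all three.
4. Keep remission prevalence ratios and numbers needed to treat as secondary, with a stated cut-off and denominator and baseline score as covariate.
5. Reconcile Study aims and the Assessment schedule on which follow-ups each arm has, and use one anchor for the 3-month visit in all arms.

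**Cost.** SAP wording and one weighted regression; if all arms already share one 3-month anchor, no new data. The headline effect is in points rather than a number needed to treat. A claim rule lowers score power as in step 4 (for example from 81% for one contrast to 75% per contrast under full Holm, or 64% for beating all three), and allowing for GCBT groups lowers it further. Remission would lose power under the same rules.
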